### **3.3.5 Infusion Reactions to Obinutuzumab**

The most frequently observed adverse drug reactions (ADRs) in patients receiving obinutuzumab were IRRs which occurred predominantly during infusion of the first 1000 mg. In patients with CLL who received the combined measures for prevention of IRRs (adequate corticosteroid, oral analgesic/anti-histamine, omission of antihypertensive medication), a decreased incidence of IRRs of all grades was observed. The rates of Grade 3-4 IRRs (which were based on a relatively small number of patients) were similar before and after mitigation measures were implemented. The incidence and severity of infusion-related symptoms decreased substantially after the first 1000 mg was infused, with most patients having no IRRs during subsequent administrations of obinutuzumab.

In the majority of patients, irrespective of indication, IRRs were mild to moderate and could be managed by the slowing or temporary halting of the first infusion, but severe and life-threatening IRRs requiring symptomatic treatment have also been reported. IRRs may be clinically indistinguishable from IgE-mediated allergic reactions (e.g., anaphylaxis). Patients with a high tumor burden and/or high circulating lymphocyte count in CLL [ $> 25 \times 10^9/L$ ] may be at increased risk of severe IRR. Rate modifications depending on the severity of IRRs are provided in the table below ([Table 18](#)).

**Table 18: Obinutuzumab infusion rate modifications for infusion-related reactions**

| Grade                            | Intervention  |
|----------------------------------|---|
| Grade 1-2
(mild and moderate) | 
Reduce infusion rate and treat symptoms.
 
Upon resolution of symptoms, continue infusion.
 
If patient does not experience any IRR symptoms, infusion rate escalation may resume at the increments and intervals as appropriate for the treatment dose (see Table 13 and Table 14).
 
For CLL patients receiving the Cycle -2, Day 1 dose split over 2 days, the Day 1 infusion rate may be increased back up to 25 mg/hr after 1 hour, but not increased further.
   |
| Grade 3
(severe)              | 
Temporarily interrupt infusion and treat symptoms.
 
Upon resolution of symptoms, restart infusion at no more than half the previous rate (the rate being used at the time that the IRR occurred). If patient does not experience any further IRR symptoms, infusion rate escalation may resume at the increments and intervals as appropriate for the treatment dose (see Table 13 and Table 14).
 
For CLL patients receiving the Cycle -2, Day 1 dose split over 2 days, the Day 1 infusion rate may be increased back up to 25 mg/hr after 1 hour, but not increased further.
 
If the patient experiences a second occurrence of a Grade 3 IRR, stop infusion and permanently discontinue therapy.
 |
| Grade 4
(life-threatening)    | Stop infusion and permanently discontinue therapy.  |

### **3.4 SAFETY MANAGEMENT GUIDELINES FOR OTHER COMMON TOXICITIES**

Guidelines for management of other common anticipated toxicities from study medications will be discussed in this section. It is emphasized that these are general guidelines and may or may not be followed depending on the patient's clinical situation and investigator's judgement. Other supportive measures which the investigator deems appropriate for the clinical situation, may be utilized. Therefore, if other measures are used, it must be documented appropriately.

#### **3.4.1 Tumor Lysis Syndrome (Venetoclax and Obinutuzumab)**

See Section [4.1.2](#)

#### **3.4.2 Magrolimab**

##### **3.4.2.1 Anemia**

Treatment with a priming dose of 1 mg/kg followed by higher weekly maintenance dosing is associated with an early, transient, acute decline in hemoglobin levels of about 2 g/dL, with nadirs occurring in most patients within the first 2 weeks of starting therapy. In most patients with adequate bone marrow reserve, hemoglobin levels gradually recover to baseline by Week 4 or later, despite continued treatment with magrolimab. Based on these data, all patients must have a documented hemoglobin  $\geq$  9 g/dL within 24 hours prior to each of the first 2 doses of magrolimab infusion during initial treatment. Patients who do not meet these criteria must be transfused and have their hemoglobin rechecked to meet  $\geq$  9 g/dL prior to each of the first 2 doses of magrolimab. For patients after exposure to magrolimab, hemoglobin will be monitored frequently for response

and/or toxicity prior to each dose, and 3 to 6 hours after the initiation of the first and second doses of magrolimab. The patient should be transfused as clinically appropriate.

Magrolimab binds to RBCs and may cause transient interference with cross-matching of units for transfusion. During the screening period, red blood cell typing per NIH CC guidelines will be performed for each patient. For all elective red cell transfusions, leukocyte-reduced units matched for the phenotype of the patients will be used. Where exact matching for all the specified blood groups proves impractical (e.g., for MNS blood group), local sites will decide on the best matched donor units to be used. Cytomegalovirus (CMV) matching (i.e., CMV-seronegative units for CMV-seronegative patients) will not be required for this study because it will limit the inventory for antigen matching.

If the crossmatch is incompatible, the RBC units that are Coombs crossmatch-incompatible will be selected (e.g., phenotype-matched or least incompatible) for issue at the discretion of the local site's Transfusion Service Medical Director or equivalent person, where available. For emergency transfusions, the transfusion laboratory may consider using emergency Group O Rhesus negative units if phenotyped units are not available. Blood plasma therapy will be blood-type specific. Platelets will be blood type compatible whenever possible, and if not, will have been tested and found not to have high titer anti-A or anti-B.

#### 3.4.2.2 Pneumonitis

Pneumonitis has been infrequently observed in patients receiving magrolimab. Generally, immune-related AEs have not been observed in clinical use with magrolimab. In contrast to T-cell checkpoint inhibitors, magrolimab primarily exerts its antitumor efficacy through macrophage-mediated phagocytosis of tumor cells. Nonspecific T-cell or other host immune responses that are seen with T-cell checkpoint inhibitors have not been observed with magrolimab in nonclinical studies. Additionally, no events of macrophage activation syndrome or hemophagocytic lymphohistiocytosis have been reported in clinical studies. In instances of suspected pneumonitis, first rule out noninflammatory causes (e.g. infections). If a noninflammatory cause is identified, treat accordingly and continue therapy per protocol. Evaluate with imaging (e.g. chest x-ray or CT) and pulmonary consultation. Management of potential pneumonitis follows ASCO guidelines for immune-related AEs. Patients who experience Grade 3 to 4 pneumonitis will be permanently discontinued from study treatment.

#### 3.4.2.3 Thromboembolic Events

Thromboembolic events, including deep vein thromboses and pulmonary embolisms, have been reported in some patients receiving magrolimab, sometimes early in therapy. Available data for magrolimab do not support a clear or consistent relationship between clinical thromboembolic events and magrolimab use. Patients should be closely monitored for the symptoms of thromboembolic events and treated accordingly.

#### 3.4.2.4 Severe Neutropenia Prophylaxis

Severe neutropenia and febrile neutropenia were reported in patients treated with magrolimab in combination with chemotherapy. Close monitoring of hematologic parameters including neutrophils is required for all patients treated with magrolimab. For patients with high risk of developing Grade 4 neutropenia and febrile neutropenia, primary and secondary prophylaxis with G-CSF is highly recommended. Prophylactic use of antimicrobials may be considered at the discretion of the treating physician. Management of neutropenia and dose modifications will be per Section [3.3.2](#).

### 3.4.2.5 Serious Infections

Patients (with or without neutropenia) should be regularly monitored for signs and symptoms of infection. For patients with prolonged neutropenia or patients at risk, consider infection prophylaxis including antibiotics (eg. fluoroquinolone) or antifungal agents (eg. oral triazoles or parenteral echinocandin) in accordance with current guidelines.

- For patients being treated for serious infections, hold the next dose of magrolimab until the infection has resolved clinically.
- For serious infections that remain active for  $\geq 14$  days, consider discontinuation of magrolimab.

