#### 4.2.1 Venetoclax and CYP3A and P-gp Inhibitors/Inducers

##### 4.2.1.1 Venetoclax Use with CYP3A and P-gp Inhibitors

Concomitant use of venetoclax with moderate to strong CYP3A inhibitors during the ramp-up phase in MZL, MCL and CLL patients is contraindicated. Concomitant use of venetoclax with CYP3A inhibitors increases venetoclax exposure and may increase the risk for TLS at initiation and during ramp-up phase. For FL patients, moderate to strong CYP3A inhibitors are contraindicated for up to 2 weeks after initiation of venetoclax. At stable doses of venetoclax, attempts must be made to avoid concomitant use of strong or moderate CYP3A or P-gp inhibitors. However, the inhibitor may be used if needed per investigator discretion, with dose modifications as outlined in **Table 20**:

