**Table 20: Management of potential venetoclax interactions with CYP3A and P-gp inhibitors**

| Inhibitors               | Ramp-Up Phase   | Patients Receiving Stable Dose of Venetoclax                      |
|--------------------------|-----------------|---|
| Strong CYP3A inhibitor   | Contraindicated | Avoid inhibitor use or reduce the venetoclax dose by at least 75% |
| Moderate CYP3A inhibitor | Contraindicated | Avoid inhibitor use or reduce the venetoclax dose by at least 50% |
| P-gp inhibitor           |                 |   |

**NOTE:** Common CYP3A and P-gp inhibitors are mentioned in [Appendix C](#).

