### **APPENDIX C: INHIBITORS AND INDUCERS OF CYP3A AND P-GP**

A comprehensive list of inhibitors can be found at the following website: <http://medicine.iupui.edu/clinpharm/ddis/table.aspx>. The general categorization into strong, moderate, and weak inhibitors according to the website and venetoclax FDA label is displayed below.

| Inhibitors of CYP3A   | Inducers of CYP3A  | Inhibitors of P-gp   |
|--|---|---|
| Strong inhibitors:
INDINAVIR
NELFINAVIR
RITONAVIR
CLARITHROMYCIN
ITRACONAZOLE
KETOCONAZOLE
NEFAZODONE
SAQUINAVIR
TELITHROMYCIN
CONIVAPTAN
POSACONAZOLE
VORICONAZOLE

Moderate inhibitors:
aprepitant
erythromycin
diltiazem
fluconazole
grapefruit juice
seville orange juice
verapamil | Weak inhibitors:
cimetidine

All other inhibitors:
amiodarone
azithromycin
chloramphenicol
boceprevir
ciprofloxacin
delavirdine
diethyl-dithiocarbamate
fluvoxamine
gestodene
imatinib
mibepradil
mifepristone
norfloxacin
norfluoxetine
star fruit
telaprevir
troleandomycin
voriconazole | carbamazepine
efavirenz
nevirapine
barbiturates
glucocorticoids
modafinil
oxcarbazepine
phenobarbital
phenytoin
pioglitazone
rifabutin
rifampin
St. John's Wort
troglitazone |

Source: <http://medicine.iupui.edu/clinpharm/ddis/table.aspx> and  
[https://www.accessdata.fda.gov/drugsatfda\\_docs/label/2016/208573s000lbl.pdf](https://www.accessdata.fda.gov/drugsatfda_docs/label/2016/208573s000lbl.pdf)

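### Section 3.4.2.5 suggests oral triazole prophylaxis without reference to the venetoclax interaction rules, which contraindicate every triazole listed in Appendix C during ramp-up, or early after venetoclax starts in FL

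*Combined protocol and SAP*

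**What the plan says.** Section 3.4.2.5 sits under the magrolimab safety guidance. For patients with lasting neutropenia, or otherwise at risk of infection, it suggests considering antibiotics or "antifungal agents (eg. oral triazoles or parenteral echinocandin) in accordance with current guidelines". Neither the sentence nor the rest of that section points to the venetoclax interaction rules. The opening of Section 3.4 says of all its contents that "these are general guidelines and may or may not be followed", depending on the clinical situation and the investigator's judgement.

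The interaction rules are in Section 4.2.1.1: "Concomitant use of venetoclax with moderate to strong CYP3A inhibitors during the ramp-up phase in MZL, MCL and CLL patients is contraindicated". The same section applies the contraindication to FL patients, who have no ramp-up, for up to two weeks after venetoclax is started. Once the venetoclax dose is stable, inhibitors are to be avoided where possible but may be used at the investigator's discretion under Table 20. For a strong inhibitor that table reads "Avoid inhibitor use or reduce the venetoclax dose by at least 75" per cent; for a moderate one the figure is 50 per cent.

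Appendix C assigns drugs to classes. Its strong list includes the adjacent entries "ITRACONAZOLE KETOCONAZOLE" and "POSACONAZOLE VORICONAZOLE". Its moderate list includes the run "diltiazem fluconazole grapefruit juice".

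**The concern.** An investigator managing a neutropenic patient would naturally turn to Section 3.4.2.5. One of its two antifungal examples is a drug group whose members, as far as Appendix C lists them, are all barred at the start of venetoclax. Nothing in that section warns of this.

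What is at stake is patient safety. Section 4.2.1.1 states that CYP3A inhibitors raise venetoclax exposure and may increase the risk of tumor lysis syndrome at the start of treatment and during ramp-up. Section 4.1.2.1 places the highest risk of that syndrome in the same five weeks. There is also an operational consequence. Section 3.10.1 makes the need for a therapy prohibited under Section 4.2 a criterion for removal from protocol therapy, so following an example in one section could bring a patient under a removal rule in another.

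**Working it through.** No statistical figure is involved, so the check sets the passages side by side.

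**Step 1. Which listed drugs are triazoles?** Appendix C does not label drugs by chemical group. Taking the ordinary drug class as an assumption, the triazoles it lists are itraconazole, posaconazole, voriconazole and fluconazole. Ketoconazole is not counted.

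**Step 2. How are they classed, and what follows?**

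| Triazole | Appendix C class | Ramp-up (MZL, MCL, CLL) | Start of venetoclax (FL) | Stable dose |
|---|---|---|---|---|
| Itraconazole | Strong | Contraindicated | Contraindicated, up to 2 weeks | Avoid, or cut venetoclax by at least 75% |
| Posaconazole | Strong | Contraindicated | Contraindicated, up to 2 weeks | Same |
| Voriconazole | Strong (listed again under other inhibitors) | Contraindicated | Contraindicated, up to 2 weeks | Same |
| Fluconazole | Moderate | Contraindicated | Contraindicated, up to 2 weeks | Avoid, or cut venetoclax by at least 50% |

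The ramp-up and stable-dose columns come from Section 4.2.1.1 and Table 20. The FL column comes from Section 4.2.1.1 alone. All four listed triazoles (3 strong + 1 moderate) fall under the restrictions.

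**Step 3. How much of Cycle 1 is affected?** Ramp-up lasts 5 × 7 = 35 days, which is the whole of Cycle 1 in Arms 2 and 4 (Tables 10 to 12). In Arm 2 it is also the whole DLT assessment period (Section 3.1.4). For FL in Arms 1 and 3 the restriction covers up to 2 × 7 = 14 of the 28 days of Cycle 1.

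**Step 4. Do other sections catch the conflict?** Only in part.

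- The exclusion criterion in Section 2.1.2.6 names strong inhibitors only, for both the ramp-up histologies and FL.
- The prohibited list in Section 4.2 also names strong inhibitors only.
- Section 4.2.1.1 and Table 20 bar strong and moderate inhibitors.

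Both narrower passages point towards Section 4.2.1, so a reader who follows the references reaches the wider rule. Read as written, however, they do not cover fluconazole. It is then unclear whether needing fluconazole early in venetoclax treatment counts as needing a prohibited therapy under Section 3.10.1.

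**Step 5. Is there a check before venetoclax is added in expansion?** Table 9 sets the conditions for starting the triplet: performance status, blood counts, renal function and transaminases. It does not ask about inhibitors, so a triazole begun during the doublet window would not be picked up there.

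**The case against.** The strongest reply is that nothing is truly contradictory. Section 3.4.2.5 only asks the investigator to consider prophylaxis, offers its drugs as examples, and names a parenteral echinocandin beside the triazoles. Section 3.4 is advisory, while Section 4.2.1.1 is specific and remains in force. The prophylaxis text also covers periods when a triazole is not contraindicated: the two-cycle window without venetoclax, and stable dosing, when use is discretionary. An investigator can therefore comply with both sections. All of this stands, and it limits the point to an unreconciled inconsistency. A reader might infer that the protocol directs investigators to give a contraindicated drug; it does not.

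Three further inferences are tempting and should not be drawn.

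- **Under-dosing in the DLT period.** For an FL patient on 800 mg, Table 20 implies 800 × (1 − 0.75) = 200 mg or less with a strong inhibitor and 800 × (1 − 0.50) = 400 mg or less with a moderate one. It does not follow that the assigned dose level goes untested. Table 20 puts avoidance first, and Section 4.2.1.1 says that inhibitors raise exposure, so 200 mg with an inhibitor cannot be read as 200 mg alone. The documents give no exposure figure that would settle the matter.
- **Frequency.** Table 6 reports grade 3 or 4 neutropenia in 112 of 212 patients (53%) on venetoclax and obinutuzumab. Those patients had previously untreated CLL, and the figure measures neither prolonged neutropenia nor antifungal use.
- **Fluoroquinolones.** Section 3.4.2.5 also gives a fluoroquinolone as an example, and Appendix C lists ciprofloxacin and norfloxacin outside the strong and moderate groups. The CYP3A rows of Table 20 restrict only those two groups, so its silence most simply means that no restriction is stated. Whether either drug needs a class is a clinical question resting on sources outside the documents.

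**Conclusion.** The inconsistency is real and bears on safety. Section 3.4.2.5 offers oral triazoles with no caveat, while all four triazoles in Appendix C belong to classes that Section 4.2.1.1 contraindicates when venetoclax is being introduced. A second disagreement lies beneath it: Sections 2.1.2.6 and 4.2 name strong inhibitors only, whereas Section 4.2.1.1 and Table 20 also cover moderate ones, and fluconazole falls in that gap.

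The exposed period is 35 of 35 days of Cycle 1 for MZL, MCL and CLL, and up to 14 of 28 days for FL. The number of patients affected cannot be estimated, because the documents give no rate of triazole use. No endpoint, sample size or analysis depends on the point. It rests on one assumption, that the four drugs are triazoles in the ordinary sense, and on Appendix C's own classification. It should be corrected because the text as it stands can mislead at the time of highest tumor lysis risk, even though a careful reader of Section 4.2.1.1 would not be misled.

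**What to change.** The sponsor should reconcile Sections 2.1.2.6, 3.4.2.5, 4.2 and 4.2.1.1, Table 20 and Appendix C, so that they agree on which inhibitor classes are restricted, in which histologies and for how long. In the same edit, Section 3.4.2.5 should cross-refer to Section 4.2.1.1 and Table 20, and the double listing of voriconazole in Appendix C should be resolved. Which rule is right is for the sponsor to decide; no drug, dose or clinical rule is proposed here.

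The cost is one cross-reference and some aligned wording in an amendment. No new data are needed, since Section 4.1 already requires concomitant medication to be recorded.

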### 3.4.3 Obinutuzumab

#### 3.4.3.1 Hypersensitivity Reactions

Hypersensitivity reactions with immediate (e.g., anaphylaxis) and delayed onset (e.g., serum sickness), have been reported in patients treated with obinutuzumab. If a hypersensitivity reaction is suspected during or after an infusion (e.g., symptoms typically occurring after previous exposure and very rarely with the first infusion), the infusion should be stopped, and treatment permanently discontinued. Patients with known hypersensitivity to obinutuzumab must not be treated. Hypersensitivity may be clinically difficult to distinguish from infusion related reactions.

#### 3.4.3.2 Worsening of Pre-existing Cardiac Conditions

In patients with underlying cardiac disease, arrhythmias (such as atrial fibrillation and tachyarrhythmia), angina pectoris, acute coronary syndrome, myocardial infarction and heart failure have occurred when treated with obinutuzumab. These events may occur as part of an IRR and can be fatal. Therefore, patients with a history of cardiac disease should be monitored closely. In addition, these patients should be hydrated with caution in order to prevent a potential fluid overload.

#### 3.4.3.3 Hepatitis B Reactivation

HBV reactivation, in some cases resulting in fulminant hepatitis, hepatic failure and death, can occur in patients treated with anti-CD20 antibodies including obinutuzumab. HBV screening should be performed in all patients before initiation of treatment with obinutuzumab. At minimum this should include HBsAg-status and HBcAb-status. These can be complemented with other appropriate markers as per local guidelines. Patients with active Hepatitis B disease should not be treated with obinutuzumab. Patients with positive hepatitis B serology should consult liver disease experts before start of treatment and should be monitored and managed following local medical standards to prevent hepatitis reactivation.

#### 3.4.3.4 Progressive Multifocal Leukoencephalopathy (PML)

PML has been reported in patients treated with obinutuzumab. The diagnosis of PML should be considered in any patient presenting with new-onset or changes to preexisting neurologic manifestations. The symptoms of PML are nonspecific and can vary depending on the affected region of the brain. Motor symptoms with corticospinal tract findings (e.g., muscular weakness, paralysis, and sensory disturbances), sensory abnormalities, cerebellar symptoms, and visual field defects are common. Some signs/symptoms regarded as “cortical” (e.g., aphasia or visual-spatial disorientation) may occur. Evaluation of PML includes, but is not limited to, consultation with a neurologist, brain MRI, and lumbar puncture (cerebrospinal fluid testing for JCV DNA). Therapy with obinutuzumab should be withheld during the investigation of potential PML and permanently

discontinued in case of confirmed PML. Discontinuation or reduction of any concomitant immunosuppressive therapy should also be considered. The patient should be referred to a neurologist for the evaluation and treatment of PML.

### **3.5 ON STUDY EVALUATIONS**

Upon successful enrollment, and following completion of the Screening/Baseline visits, patients will begin treatment as outlined in Section [3.1](#). The results from all procedures/tests must be reviewed prior to initiation of each cycle of treatment for consideration of dose modifications.

Treatment with magrolimab, obinutuzumab, and venetoclax will continue until discontinuation per study protocol (Section [3.1](#)), disease progression, unacceptable treatment-related toxicity, or other reasons outlined in Section [3.9](#). Refer to the Study Calendar ([Appendix G](#)) for additional information for all tests and procedures to be performed prior to each visit and in follow-up.

